11.11. Interim and Planned Analyses

A single Interim Analysis was performed by the ISC after all enrolled patients completed the Week 16 visit, the timepoint for the primary efficacy evaluation of interest. The unblinded results of the Interim Analysis were prepared for select Sponsor representatives, to facilitate the dose selection. The Sponsor and CRO's study operational team will remain blinded to the individual patient treatment assignment. Investigators and study patients will remain blinded to the randomized treatment assignment until all patients complete their Week 48, post-baseline biopsy visit. Upon completion of the study, Investigators and study patients will be informed of the patient's randomized treatment assignment from the double-blinded phase.

In order to maintain a complete audit trail of activities related to the Interim Analysis and to secure a controlled access to interim results, the study will utilize a controlled access execution system for storage and distribution of Interim Analysis related documents.

A detailed Data Access Plan outlining which parties will have access to which data and at what time will be prepared. The plan will further indicate which study functions or parties have access to either individual patient or aggregate group treatment information, and/or the selected dose over the duration of the study.

The Extended Efficacy Analysis will be performed after the last patient with fibrosis finish post-baseline biopsy visit. The Final Analysis will be performed once all patients complete an Early Termination or Study Completion visit and database lock.

11.12. Data Recording and Quality Control

Source documents must be maintained for each patient in the study, consisting of all demographic and medical information, including clinical laboratory data, etc. A copy of the signed ICF must be retained. All information on the eCRFs must be traceable to these source documents in the patient's file.

Data recorded in all patients' eCRFs will be subjected to a quality control review.

12. STUDY APPROVAL AND CONDUCT

The following conditions will be met.

12.1. Regulatory Approval

The requirements for the conduct of clinical trials in accordance with local applicable regulations will be met before commencement of this study.

12.2. Institutional Review Board (IRB)/Ethics Committee (EC) Approval

Prior to initiation of the study, written IRB/EC approval of the Protocol and ICFs, based on the principles of ICH cGCP procedures, will be received. A copy of the signed and dated letter of approval will be provided to the clinical site and Arrowhead Pharmaceuticals, Inc. prior to study commencement. Any written information and/or advertisements to be used for volunteer recruitment will be approved by the IRB/EC prior to use. A list of the IRB/EC voting members, their titles or occupations, Federalwide Assurance number (where applicable) and their institutional affiliations will be requested before study initiation.

Protocol modifications that may impact patient safety or the validity of the study will be approved by the IRB/EC, following written agreement from the Sponsor.

12.3. Ethical Considerations

This study will be carried out per the Declaration of Helsinki 1964, as modified by the 64th World Medical Assembly, Fortaleza, Brazil, October 2013, the Notes for Guidance on Good Clinical Practice (cGCP) (2000) (CPMP/ICH/135/95), and the Principles of the ICH cGCP. The protocol will be submitted for approval to the IRB/EC, and written approval obtained before patients are enrolled. The composition of the IRB/EC will also be provided to the Sponsor. If approval is suspended or terminated by the IRB/EC, the Investigator will notify the Sponsor immediately.

Where applicable, the clinical site and Arrowhead Pharmaceuticals, Inc. agree to abide by the local compensation guidelines for injury resulting from participating in a company-sponsored research project. Compensation will only be provided on the understanding that the provision of compensation does not amount to an admission of legal liability and is subject to the proposed recipient signing a full and complete release of the company from all claims, damages, and costs.

12.4. Written Informed Consent

Informed consent will be obtained before the patient can participate in the study. The contents and process of obtaining informed consent will be in accordance with all applicable regulatory requirements. Study participation includes all Screening procedures, as well as any washout of excluded medications.

It is the responsibility of the Investigator (or medically qualified designee) to obtain a written informed consent from everyone participating in this study after adequate explanation of the aims, methods, objectives, and potential hazards of the study. The Investigator (or medically qualified designee) must also explain to the patients that they are completely free to refuse to enter the study or to withdraw from it at any time. Appropriate forms for documenting a written consent will be provided by the Investigator or by Arrowhead Pharmaceuticals, Inc.

For this study, each eligible patient will be required to provide written informed consent before participation in the study.

All eligible patients will have the study explained by the Investigator or designee. They will receive a full explanation, in lay terms, of the aims of the study, the discomforts, risks and benefits in taking part as well as of insurance and other procedures for compensation in case of injury. It will be explained that the study is for research purposes only and is not expected to provide any therapeutic benefit to the individual. It will be pointed out that they can withdraw from the study at any time without prejudice. Each patient will acknowledge receipt of this information by giving written informed consent for participation in the study. The volunteer will be given a copy of the signed ICF to retain.

12.5. Emergency Contact with Principal Investigator

Suitable arrangements will be made for patients to contact the Investigator or medically trained designee in the event of an emergency.

12.6. Notification of General Practitioner

It is the responsibility of the Principal Investigator (PI) or designee, to notify, where applicable, with the consent of the patient, the general practitioner of the patient's participation in the trial, by sending a letter stating the nature of the trial, treatments, expected benefits or AEs and concomitant drugs to be avoided.

12.7. Clinical Laboratory Certification and Reference Ranges

Before the initiation of this study, the PI, or designee, will obtain a copy of the certification form, with certification number and expiration date for all clinical laboratories (excluding central laboratories) used in the study. Reference ranges for each clinical laboratory test used in this study will be obtained from the appropriate laboratory, which will perform the test for the study.

12.8. Protocol Deviations

A protocol deviation is defined as any intentional or unintentional change to, or noncompliance with, the approved protocol procedures or requirements. The PI will conduct the study in compliance with the approved protocol and will not implement any deviation from or changes to the protocol without prior agreement by the Sponsor and review and documented approval from the regulatory authorities and IRB/EC of an amendment, except where necessary to eliminate an immediate hazard to study patients.

Deviations may result from the action or inaction of the patient, PI, or site staff. Examples of deviations include, but are not limited to:

- Failure to adhere to study exclusion and inclusion criteria
- Failure to comply with dispensing or dosing requirements
- Use of medications, food, drink, herbal remedies, or supplements that are specifically prohibited in the protocol
- Missed or out-of-window visits
- Drug dosing not administered within the time frame specified in the protocol
- Failure to adhere to test requirements, including vital signs, laboratory tests, physical examinations, PK blood draws, medical history, etc. either tests not done, incorrect tests done, or not done within the time frame specified in the protocol
- Procedural deviations such as incorrect storage of study drug, failure to update the ICF when new risks become known, failure to obtain IRB/EC approvals for the protocol and ICF revisions

Protocol deviations impacting patient safety or eligibility will be reported to the Sponsor or CRO within two (2) business days of occurrence and to the IRB/EC/competent regulatory authority per local regulatory requirements.

The Investigator is responsible for ensuring that any known protocol deviations are recorded and reported as agreed. The nature and reasons for protocol deviations will be recorded in each patient's eCRF.

12.9. Termination of the Study

The Sponsor reserves the right to discontinue the trial at any time. Reasons will be provided in the event of this happening. The Investigator reserves the right to discontinue the study for safety reasons at any time in collaboration with the Sponsor.

13. STUDY ADMINISTRATION

13.1. Study Monitoring

Arrowhead Pharmaceuticals, Inc. is responsible for assuring the proper conduct of the study about protocol adherence and validity of the data recorded in the eCRFs. Patient confidentiality will be maintained.

In accordance with applicable regulations, cGCP, and Arrowhead Pharmaceuticals, Inc. procedures, Arrowhead Pharmaceuticals, Inc. will be responsible for assigning a study monitor (CRA) who will contact the site to organize a visit prior to patient enrolment to review the protocol and data collection procedures with site staff. In addition, the assigned study monitor will periodically contact the site, including conducting on-site visits. The extent, nature and frequency of on-site visits will be based on such considerations as the study objective and/or endpoints, the purpose of the study, study design complexity, and enrollment rate.

During these site visits, the study monitor will:

- Check the progress of the study
- Review study data collected
- Conduct source document verification
- Identify any issues and address their resolution
- Check investigational product accountability
- Review blood and urine samples and ensure they are labeled and stored correctly

This will be done to verify that the:

- Data are authentic, accurate and complete
- Safety and rights of patients are being protected
- Study is conducted in accordance with the currently approved protocol (and any amendments), cGCP and all applicable regulatory requirements

The PI agrees to allow the monitor direct access to all relevant documents and to allocate his/her time and the time of his/her staff to the monitor to discuss findings and any relevant issues.

At study closure, a study monitor will conduct the following activities in conjunction with the PI or site staff as appropriate:

• Return of all study data to Arrowhead Pharmaceuticals, Inc.

- Data queries
- Accountability, reconciliation, and arrangements for unused investigational product(s)
- Inventory and final disposition (e.g., destruction, shipping to repository, etc.)
- Review of site study records for completeness

Because the study is blinded, an unblinded study monitor will be assigned to visit the site pharmacy during, and at Study Completion to review the randomization schedule in comparison to the dispensing log to verify correct randomization of study drug.

13.2. Quality Assurance

To ensure compliance with cGCP and all applicable regulatory requirements, Arrowhead Pharmaceuticals, Inc. may conduct a quality assurance audit of the study site. Regulatory agencies may also conduct a regulatory inspection of this study. Such audits/inspections can occur at any time during or after completion of the study. If an audit or inspection occurs, the PI and clinical site agree to notify Sponsor as soon as possible following awareness of an impending regulatory inspection. The PI and clinical site agree to allow the auditor/inspector direct access to all relevant documents and allocate his/her time and the time of his/her staff to the auditor/inspector to discuss findings and any relevant issues.

13.3. Records Retention

Following closure of the study, the PI must maintain all site study records in a safe and secure location. The records must be maintained to allow easy and timely retrieval, when needed (e.g., audit or inspection) and whenever feasible, to allow any subsequent review of data in conjunction with assessment of the facility, supporting systems and staff. When permitted by local laws/regulations or institutional policy, some of these records can be maintained in a format other than hard copy (e.g., microfiche, scanned, electronic); however, caution needs to be exercised before such action is taken. The PI must assure that all reproductions are legible and are a true and accurate copy of the original and meet accessibility and retrieval standards, including re-generating a hard copy, if required. Furthermore, the PI must ensure there is an acceptable back-up of these reproductions and that an acceptable quality control process exists for making these reproductions.

Arrowhead Pharmaceuticals, Inc. will inform the PI of the time period for retaining these records to comply with all applicable regulatory requirements. The minimum retention time will meet the strictest standard applicable to that site for the study, as dictated by any institutional requirements or local laws or regulations, or Arrowhead Pharmaceuticals, Inc. standards/procedures; otherwise, the retention period will default to 15 years.

The material to be stored shall include, but is not limited to, the following:

- Signed and dated copy of the final study protocol and any amendments
- Signed and dated letter of IRB/EC approval, letter of constitution of the IRB/EC and copies of any other correspondence relevant to the study with the IRB/EC or regulatory authorities
- The IRB/EC approved ICF
- Current *curriculum vitae* (signed and dated) of the PI and co-workers with major responsibilities in the trial
- Site Signature and Delegation of Responsibility Log
- Food and Drug Administration (FDA) Form 1572 (where applicable)
- Financial Disclosure Form(s)
- Blank case report form/eCRF
- Signed patient ICFs
- Laboratory reference ranges (signed and dated)
- The completed Clinical Trial Notification (CTN) Application Form (where applicable)
- The Final Study Report
- Clinical raw data including the Source Data Forms, all clinical laboratory report forms, patient eCRFs, drug accountability forms, and dispensing records, etc.

14. INFORMATION DISCLOSURE AND INVENTIONS

14.1.	Ownership
14.2.	Confidentiality
14.3.	Publication

APPENDIX 1: METABOLIC SYNDROME CRITERIA

Metabolic syndrome in this study will be defined as having at least 3 of the identified risk factors (Alberti et al., 2009).

Table 1. Criteria for Clinical Diagnosis of the Metabolic Syndrome

Measure	Categorical Cut Points
Elevated waist circumference*	Population- and country-specific definitions
Elevated triglycerides (drug treatment for elevated triglycerides is an alternate indicator†)	≥150 mg/dL (1.7 mmol/L)
Reduced HDL-C (drug treatment for reduced HDL-C is an alternate indicator†)	<40 mg/dL (1.0 mmol/L) in males; <50 mg/dL (1.3 mmol/L) in females
Elevated blood pressure (antihypertensive drug treatment in a patient with a history of hypertension is an alternate indicator)	Systolic ≥130 and/or diastolic ≥85 mm Hg
Elevated fasting glucose‡ (drug treatment of elevated glucose is an alternate indicator)	≥100 mg/dL

HDL-C indicates high-density lipoprotein cholesterol.

*It is recommended that the IDF cut points be used for non-Europeans and either the IDF or AHA/NHLBI cut points used for people of European origin until more data are available.

†The most commonly used drugs for elevated triglycerides and reduced HDL-C are fibrates and nicotinic acid. A patient taking 1 of these drugs can be presumed to have high triglycerides and low HDL-C. High-dose ω -3 fatty acids presumes high triglycerides.

\$\pmox{Most patients with type 2 diabetes mellitus will have the metabolic syndrome by the proposed criteria.

APPENDIX 2: ELEVATED ALT OR WORSENING HEPATIC FUNCTION STUDY MODIFICATION AND PATIENT DISCONTINUATION RULES

Treatment-Emergent ALT	Treatment-Emergent Total Bilirubin (TBL)	Liver Symptoms	Action	
Normal baseline: ALT >5× ULN	Normal	None	Repeat ALT, AST, ALP, TBL, in 2–3 days	
Elevated baseline: ALT >3× baseline or >300 U/L			Follow-up for symptoms.	
(whichever occurs first)				
Normal baseline: ALT >8× ULN	Normal	None	Interrupt study drug. Initiate close observation and workup for competing etiologies. (see below)	
Elevated baseline: ALT >5× baseline or >500 U/L				
(whichever occurs first)			Study drug can be restarted only if an alternative etiology is identified and liver enzymes return to baseline.	
Normal baseline: ALT >3× ULN	TBL >2× ULN	None	Interrupt study drug. Initiate close observation and workup for competing etiologies.	
Elevated baseline: ALT >2× baseline or >200 U/L			Study drug can be restarted	
(whichever occurs first)			only if an alternative etiology is identified and liver enzymes return to baseline.	
Normal baseline: ALT >3× ULN	Normal or elevated	Symptoms of clinical hepatitis - severe fatigue, nausea, vomiting,	Interrupt study drug. Initiate close observation and workup for competing etiologies.	
Elevated baseline: ALT >2× baseline or >200 U/L			Study drug should not be	
(whichever occurs first)		right upper quadrant pain	restarted	

ALP=alkaline phosphatase; ALT= alanine aminotransferase; AST= aspartate aminotransferase; TBL=total bilirubin. Source: Adapted from Chalasani, Naga and Regev, Arie et al. Drug-Induced Liver Injury in Subjects with Preexisting Chronic Liver Disease in Drug Development: How to Identify and Manage? Gastroenterology, Volume 151, Issue 6, 1046 – 1051

Close observation for potential drug-induced liver injury (DILI):

Within 72 hours, perform a complete history, physical, and liver biochemistries, including evaluation of:

- New or worsening signs and symptoms of clinical hepatitis such as fatigue, nausea, vomiting, right upper quadrant pain or tenderness, fever, rash, or eosinophilia
- Concomitant medications, including acetaminophen, dietary supplements, herbal remedies, over-the-counter medications, recreational drug use, and special diets
- Alcohol consumption
- Exposure to environmental chemical agents
- Past medical history
- Complete review of systems
- Liver biochemistries including alanine aminotransferase (ALT), aspartate aminotransferase (AST), alkaline phosphatase (ALP), gamma-glutamyl transferase (GGT), total bilirubin, direct bilirubin, and international normalized ratio (INR)
- Ruling out acute viral hepatitis type A, B C D and E; autoimmune or alcoholic hepatitis; nonalcoholic steatohepatitis (NASH); hypoxic/ischemic hepatopathy; and biliary tract disease (abdominal ultrasound).
- Consider gastroenterology or hepatology consultations

Evaluate patients 2 or 3 times a week for signs and symptoms of clinical hepatitis and obtain liver biochemistries until biochemistries stabilize or the trial drug has been discontinued and the patient is asymptomatic. If biochemistries stabilize and the patient is asymptomatic, monitor liver biochemistries once a week until they return to baseline. Analysis of such biochemistries may occur at local lab.

If the baseline liver enzymes are normal, follow the FDA guidance on "Drug- Induced Liver Injury: Premarketing Clinical Evaluation" for monitoring and managing patients if the patients experience elevations in liver enzymes during the clinical trial.

Patients who live far from study sites may be evaluated locally for history, physical exam, and laboratories, if the results are communicated promptly to the site Investigator.

Additional laboratory criteria to detect DILI:

• Interrupt the treatment and initiate DILI evaluation if:

- O Alkaline phosphatase (ALP)>2x ULN and direct bilirubin (DB) >2x ULN, if ALP and DB are normal at baseline
- \circ ALP >2x baseline and DB >2x baseline if they are elevated at baseline
- ALP >2x baseline and DB >2x baseline and symptoms consistent with clinical hepatitis
- In the event of liver enzyme elevation, perform a DILI evaluation. If a clear etiology is established to account for the liver enzyme abnormalities, and the liver enzymes return back to baseline, the study drug may be restarted.
- If upon rechallenge, any magnitude of liver enzyme elevation recurs, the patient should cease the treatment drug and should be followed in the study. If a patient cannot be followed with laboratory or clinical monitoring, rechallenge should not be performed.

Stopping rule for progression to cirrhosis during the study:

APRI (using 40 U/L as ULN) will be calculated per SOA at baseline, Day 113 (Week 16), then every other dosing day (approximately every 168 days) or earlier if development of cirrhosis is suspected clinically, which may include development of varices, decompensating events or new thrombocytopenia and splenomegaly. Any increase from baseline to an APRI value >2.0 (must be confirmed on repeat) will trigger liver biopsy. For patients with baseline APRI >2.0 but who are eligible based on pre-dose biopsy, APRI will be calculated per SOA and a \geq 50% increase from baseline (must be confirmed on repeat) will trigger liver biopsy.

Investigator may elect to confirm an elevated APRI as a biomarker of cirrhosis with MRE if available PRIOR to proceeding to biopsy. If MRE is NOT consistent with cirrhosis then biopsy is not indicated and the patient may stay on study. Alternatively, the Investigator may elect to proceed directly from APRI to biopsy.

If cirrhosis is detected on liver biopsy the patient will be discontinued from treatment and followed through EOS per SOA. This biopsy will represent EOS biopsy for purposes of endpoint determination. If cirrhosis is not confirmed on liver biopsy, patient may continue on treatment.

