6.3. DSMB and Stopping Rules

An independent DSMB consisting of 2 hepatologists and a pulmonologist and aided by an unblinded biostatistician will review the unblinded data generated from this study after the first 18 patients have received at least one dose of study drug and completed the Week 16 visit, or as needed in emergent safety related circumstances. An independent statistical center (ISC) will provide unblinded comparative safety summaries to the DSMB in a restricted manner. The Sponsor will not have access to the unblinded summaries. This planned safety review will include evaluations for imbalances between active and placebo groups for pulmonary AEs as well as clinically significant adverse changes in FEV₁ and DLCO. The DSMB may be asked to review safety data at additional unscheduled meetings should a potential safety signal be detected. The DSMB will also be involved in decisions to evaluate individual patients for discontinuation (See study modification rules in Appendix 2 and Appendix 3). The DSMB may also make recommendations regarding modification of individual study cohorts and/or study design.

A decision to stop the trial early or discontinue drug in an individual patient or group of patients may be indicated based on any of the following:

- 1. In the case of 2 or more similar serious adverse events (SAEs) both considered at least possibly related to fazirsiran, the DSMB will meet within 3 days of the DSMB being notified of the second event and within the timeframe of required regulatory agency notification. The DSMB will review available aggregated data to determine if the study remains safe to proceed, should be discontinued, or should continue but with amendments.
- Evaluation and fazirsiran study modification/discontinuation rules for elevated liver tests signaling worsening AATD liver disease or drug induced liver injury (DILI) are provided in Appendix 2.
- 3. Evaluation and fazirsiran study modification/discontinuation rules for declines in pulmonary function are provided in Appendix 3.

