Any discontinued patient will be followed with appropriate assessments and monitoring (either per SOA or with more intensive evaluation) through EOS. Sponsor or Investigator can discontinue any patient at any time with or without DSMB consultation. If such events (as described in #1 through #3 above) occur and the patient is not discontinued from the study, the reason for not discontinuing the patient will be included in DSMB meeting minutes. Including, but not limited to the events listed above, the DSMB may pause the study to additional dosing to provide time to evaluate safety data and recommend the action to be taken, which may include, but is not limited to, one of the following:

- Discontinuation of a patient or group of patients from the study
- The study is stopped immediately with no further dosing
- The study will continue, but using a lower dose
- The study will continue as planned

Arrowhead will notify the concerned regulatory agencies and ethics committees immediately and at least within 15 days from when the trial is temporarily halted or prematurely discontinued. A substantial protocol amendment will be submitted to the concerned regulatory agencies clearly explaining the reasons and scope, e.g., stopping recruitment and/or interrupting treatment of all patients already included. Furthermore, to restart the trial, the request will be submitted in form of a substantial amendment providing evidence that it is safe to restart the trial. If Arrowhead decides not to recommence a temporarily halted trial, the concerned regulatory agency(-ies) will be notified within 15 days of this decision, providing a brief explanation of the reasons for ending the trial.

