7.3. Exclusion Criteria

A potential patient will be excluded from the study if any of the following criteria apply:

- 1. INR ≥1.2 at Screening (one retest permitted). If based on opinion of Investigator and/or prescribing physician patient is appropriate for anticoagulant holiday, patient may stop taking anticoagulant for an appropriate washout period and if indicated a repeat INR within <1.2 would be acceptable. Vitamin K may be used for reversal. If INR is not indicated (direct thrombin inhibitors or Xa inhibitors) then appropriate washout period alone may be acceptable. (Note: Anti-platelet agents, aspirin, clopidogrel or nonsteroidal anti-inflammatory drugs [NSAIDs] are acceptable but must be held 7 days before and 7 days after liver biopsy)
- 2. Platelet count $<150 \times 10^9/L$ at Screening (one retest permitted)
- 3. ALT and AST levels >250 U/L at Screening (one retest permitted)
- 4. Estimated glomerular filtration rate (eGFR) <60 mL/min/1.73m² at Screening (one retest permitted)
- 5. FEV₁ <65% of predicted (preferentially post-bronchodilatory reading) at Screening (one retest permitted)
- 6. Recent (last 3 months) pneumonia or lower respiratory infection (which must be verifiable from the medical record). Patient reported infection is not sufficient to meet this criterion.
- 7. Unavoidable exposure to inhaled environmental toxins that in the clinical judgment of the Investigator could impair pulmonary function significantly over the course of the study.

- 8. Human immunodeficiency virus (HIV) infection, as shown by the presence of anti-HIV antibody (sero-positive)
- 9. Seropositive for HBV (HBsAg positive at Screening) or HCV (detectable HCV RNA at Screening). Cured HCV (positive antibody test without detectable HCV RNA is acceptable).
- 10. Uncontrolled hypertension (Systolic BP >170 and diastolic blood pressure [BP] >100 mmHg at Screening). Patients may rescreen once BP is successfully controlled.
- 11. A history of torsades de pointes, ventricular rhythm disturbances (e.g., ventricular tachycardia or fibrillation), untreated heart block (excluding first-degree block, being PR interval prolongation only), congenital long QT syndrome or new acute ST segment elevation or depression or new acute Q wave on ECG. Stable atrial dysrhythmias (e.g., stable atrial fibrillation) are acceptable.

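### Appendix 2 orders a dose interruption for a large asymptomatic ALT rise at normal bilirubin and above 2× ULN, but no row covers elevated-baseline patients in between

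*Protocol*

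**What the plan says.** The Appendix 2 table has four rows. For a patient with elevated baseline ALT they read as follows; where two ALT limits are given, the one reached first applies.

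| Row | ALT above | TBL | Symptoms | Action |
|---|---|---|---|---|
| 1 | 3× baseline or 300 U/L | Normal | None | Repeat tests |
| 2 | 5× baseline or 500 U/L | Normal | None | Interrupt |
| 3 | 2× baseline or 200 U/L | >2× ULN | None | Interrupt |
| 4 | 2× baseline or 200 U/L | Normal or elevated | Clinical hepatitis | Interrupt, no restart |

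The row 2 threshold is written "Elevated baseline: ALT >5× baseline or >500 U/L". Rows 2 and 3 allow restart only after another cause is found and enzymes are back at baseline.

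The text after the table adds:

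- a work-up: "Within 72 hours, perform a complete history, physical, and liver biochemistries, including evaluation of" a list of causes and tests;
- a pointer for some patients: "If the baseline liver enzymes are normal, follow the FDA guidance on" drug-induced liver injury (DILI);
- an interruption rule based on ALP and direct bilirubin together;
- a general bullet: "In the event of liver enzyme elevation, perform a DILI evaluation". If a clear cause is found "and the liver enzymes return back to baseline, the study drug may be restarted".

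Section 6.3 introduces these rules permissively: a decision to stop the trial or "discontinue drug in an individual patient or group of patients may be indicated based on any of the following". It lets the sponsor or investigator discontinue anyone at any time. If a listed event occurs and the patient stays in the study, "the reason for not discontinuing the patient will be included in DSMB meeting minutes".

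Patients with raised ALT can enroll. Exclusion criterion 3 in Section 7.3 removes only those with "ALT and AST levels >250 U/L at Screening (one retest permitted").

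**The concern.** A hepatic safety rule should not become less strict as bilirubin rises. Read literally, this one does. At row 2-level ALT in an asymptomatic patient, the explicit interruption applies at normal TBL, disappears once TBL passes normal, and returns above 2× ULN. The documents give no reason for the break. Row 4 shows that the drafters could include intermediate bilirubin when they wanted to.

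The gap falls on patients the rules were meant for. Section 4.8 presents stopping rules for patients with elevated baseline ALT as a mitigation of hepatic risk. What is left open is whether the next dose must wait for an identified cause and for enzymes to return to baseline. Sites could answer that differently.

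**Working it through.** There is no plan figure to reproduce. The check is whether the rows cover every combination.

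**Inputs.** ALT, TBL and symptom conditions come from the Appendix 2 table. Assumptions: normal TBL means ≤1× ULN, and the TBL value is a treatment-emergent one, as the column heading says. The baselines are illustrative, because the protocol gives no ALT ULN. The upper value of 250 U/L is the highest that exclusion criterion 3 clearly allows.

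**Thresholds.** For elevated baseline b, the limit reached first is the smaller one:

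- row 1: min(3b, 300)
- row 2: min(5b, 500)
- row 3: min(2b, 200)

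| b (U/L) | Row 1 | Row 2 | Row 3 |
|---|---|---|---|
| 60 | 180 | 300 | 120 |
| 80 | 240 | 400 | 160 |
| 100 | 300 | 500 | 200 |
| 250 | 300 | 500 | 200 |

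The row 3 limit is always below the row 2 limit. Any ALT that meets row 2 therefore also meets row 3 once TBL exceeds 2× ULN, and interruption applies on both sides of the band.

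**Action by bilirubin, asymptomatic, text as written.**

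| b, ALT (U/L) | TBL 1.0× | 1.01× | 1.5× | 2.0× | 2.1× ULN |
|---|---|---|---|---|---|
| 60, 320 | interrupt | no row | no row | no row | interrupt |
| 80, 420 | interrupt | no row | no row | no row | interrupt |
| 100, 600 | interrupt | no row | no row | no row | interrupt |
| 250, 520 | interrupt | no row | no row | no row | interrupt |

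With row 2's TBL cell set to ≤2× ULN, all five columns read interrupt in every line.

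**Side effects of the fix.** Take a grid of b from 60 to 250 by 10 (20 values), ALT from 60 to 1000 by 10 (95 values) and TBL from 0.5 to 4.0× ULN by 0.05 (71 values).

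- All cells: 20 × 95 × 71 = 134,900.
- Of the 71 TBL values, 20 lie above 1.0 and up to 2.0× ULN, and 51 lie outside. Cells outside the band: 20 × 95 × 51 = 96,900.
- ALT values above the row 2 limit: 70, 65, 60 and 55 at b = 60, 70, 80 and 90, and 50 at each of the 16 baselines from 100 to 250. Sum: 250 + 800 = 1,050. Times 20 TBL values gives 21,000 in-band cells that move from no row to interrupt.
- Outside the band, 0 of 96,900 cells change.

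A further 7,600 in-band cells are at row 1 level. They change, from no row to repeat tests, only if row 1 is edited as well. These counts describe the rule, not how often patients fall in the band.

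**Time to the next dose.** Regular dosing visits are 12 weeks (84 days) apart. Biopsy visits with laboratory tests at Week 48, 72 or 96 come 4 weeks (28 days) before the dose at Week 52, 76 or 100. A 72-hour work-up would normally finish first in either case.

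**The case against.** The strongest reply is that the rest of Appendix 2 already handles this patient. The general bullet has no bilirubin condition, requires a DILI evaluation, and sets restart conditions close to row 2's. A drug that may be restarted has presumably been stopped. The close-observation text adds the 72-hour work-up, review two or three times a week, then weekly tests until values return to baseline. Section 6.3 allows discontinuation at any time. A sensible investigator would probably treat row 2 as a minimum and hold the drug.

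Much of this stands, and it is why the point is small. It does not close the gap. The bullet orders an evaluation, not a hold, and gives no ALT threshold. Read as a hold at any elevation, it would override row 1, which only repeats tests. Where the appendix wants an interruption it says so, as in the ALP and direct bilirubin rule, but that rule is not driven by ALT. The Section 6.3 discretion is permissive, and its duty to minute attaches to events the rules describe, so it may not reach a combination that no row describes.

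Two limits on scope also stand. A patient with a stable, mildly raised pre-treatment TBL has no treatment-emergent rise and may fit row 2 already. Patients without fibrosis receive only two doses, on Day 1 and at Week 4; all enrolled patients have passed Week 16 (Section 6.1), so these patients have no dose left to interrupt.

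A reader might infer more than the documents support:

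- *That patients in the band are left unmonitored or would be dosed through liver injury.* The required evaluation and work-up rule out the first, and nothing directs the second.
- *That normal-baseline patients have the same complete gap.* They share the table gap but are also sent to the FDA guidance.
- *That the loss of row 1's repeat test matters equally.* The evaluation and work-up largely cover it.

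**Conclusion.** The concern holds as a minor defect in a safety rule. In an asymptomatic elevated-baseline patient with ALT above 5× baseline or 500 U/L, a treatment-emergent TBL above normal and up to 2× ULN matches no row, although lower and higher TBL both lead to interruption. No other text orders an ALT-based hold for that patient.

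The conclusion rests on reading normal TBL as ≤1× ULN and on the literal row conditions. Exposure is limited to patients with fibrosis who are still being dosed (planned minimum 24 of about 36). Within that group it needs an elevated baseline, a large ALT rise, no symptoms and intermediate bilirubin at the same time. The documents give no frequency, and the combination is probably rare. The primary endpoint, alpha and power are unaffected.

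**What to change.** In Appendix 2, change the TBL cell of row 2 from normal to ≤2× ULN. This alone closes the gap, and because the cell is shared it does the same for normal-baseline patients. Two additions are optional: the same edit in row 1 for consistency, and a sentence saying that the most stringent action applies when more than one row matches.

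Sections 12.2 and 12.8 call for IRB/EC approval of such a change, so a memo to sites is not enough. It can go into the next amendment and be communicated to sites then. It adds no new type of test or visit. The downside is possibly a few more dose holds, including for benign mild bilirubin rises that coincide with a large ALT rise.
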